14.5 Appendix 5: Data Display Standards & Handling Conventions

14.5.1 Reporting Process

Software

The currently supported versions of SAS and WinNonlin software will be used.

Analysis Datasets

- Analysis datasets will be created according to AdaM IG Version 1.1.
- For creation of ADaM datasets (ADCM/ADAE), the same version of dictionary datasets will be implemented for conversion from SI to SDTM.
- Define XML Version 2.0

Generation of RTF Files

RTF files will be generated for Tables, Listings, and Figures, one RTF file per item.

14.5.2 Reporting Standards

General

- The current GSK Integrated Data Standards Library (IDSL) will be applied for reporting, unless otherwise stated:
 - 4.03 to 4.23: General Principles
 - 5.01 to 5.08: Principles Related to Data Listings
 - 6.01 to 6.11: Principles Related to Summary Tables
 - 7.01 to 7.13: Principles Related to Graphics
- Do not include participant level listings in the main body of the GSK Clinical Study Report. All
 participant level listings should be located in the modular appendices as ICH or non-ICH
 listings

Formats

- GSK IDSL Statistical Principles (5.03 & 6.06.3) for decimal places (DP's) will be adopted for reporting of data based on the raw data collected.
- Numeric data will be reported at the precision collected on the eCRF.
- The reported precision from non eCRF sources will follow the IDSL statistical principles but may be adjusted to a clinically interpretable number of decimal places (DP's).

Planned and Actual Time

- Reporting for tables, figures and formal statistical analyses:
 - Planned time relative to dosing will be used in figures, summaries, statistical analyses and calculation of any derived parameters, unless otherwise stated.
 - The impact of any major deviation from the planned assessment times and/or scheduled visit days on the analyses and interpretation of the results will be assessed as appropriate.
- Reporting for Data Listings:
 - Planned and actual time relative to study drug dosing will be shown in listings (Refer to IDSL Statistical Principle 5.05.1).
 - Unscheduled or unplanned readings will be presented within the participant's listings.

Unscheduled Visits

Unscheduled visits will not be included in summary tables and/or figures.				
All unscheduled visits will be included in listings.				
Descriptive Summary	Descriptive Summary Statistics			
Continuous Data	Refer to IDSL Statistical Principle 6.06.1			
Categorical Data N, n, frequency, %				
Graphical Displays				

- Refer to IDSL Statistical Principals 7.01 to 7.13
- The same symbol and line type will be used across figures to represent a given treatment group. The placebo group will be displayed using symbol type=empty circle and line type= solid line and color=black.
- When line plots are presented with treatment groups overlaid, the x-values will be offset (jittered) so the data are not plotted on top of each other.
- X-axis variables of time and dose will be plotted as continuous numeric variables...

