9.4.5. Clinical Safety Laboratory Assessments

- Refer to Section 12.2, Appendix 2 for the list of clinical laboratory tests to be performed and to the Schedule of Assessments (Table 2 and Table 3) for the timing and frequency.
- The Investigator must review the laboratory report, document this review, and record any clinically relevant changes occurring during the study in the AE section of the CRF. The laboratory reports must be filed with the source documents. Clinically significant abnormal laboratory findings are those which are not associated with the underlying disease, unless judged by the Investigator to be more severe than expected for the participant's condition.
- All laboratory tests with values considered clinically significantly abnormal during participation in the study or within 7 days after the last dose of study treatment should be repeated until the values return to normal or baseline or are no longer considered significantly abnormal by the Investigator or medical monitor.
- If such values do not return to normal/baseline within a period of time judged reasonable by the Investigator, the etiology should be identified and the sponsor notified.

• All protocol-required laboratory assessments, as defined in Section 12.2, Appendix 2, must be conducted in accordance with the laboratory manual and the Schedule of Assessments (Table 2 and Table 3).

205820

• If laboratory values from non-protocol specified laboratory assessments performed at the institution's local laboratory require a change in participant management or are considered clinically significant by the Investigator (e.g., SAE or AE or dose modification), then the results must be recorded in the CRF.

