12.3. Appendix 3: Liver Safety: Required Actions and Follow-up Assessments

Phase 1 Liver chemistry stopping criteria have been designed to assure participant safety and to evaluate liver event etiology (in alignment with the FDA premarketing clinical liver safety guidance).

http://www.fda.gov/downloads/Drugs/GuidanceComplianceRegulatoryInformation/Guidances/UCM174090.pdf.

Phase I liver chemistry stopping criteria and required follow up assessments

Liver Chemistry Stopping Criteria				
bilirubin) or INR > 1.5, Re	ALT \geq 3 x ULN AND bilirubin ^{1,2} \geq 2 x ULN (> 35% direct bilirubin) or INR > 1.5, Report as an SAE. See additional Actions and Follow Up Assessments listed below			
Required Actions and Follow up Assessme	nts			
Actions	Follow Up Assessments			
 Report the event to GSK within 24 hours Complete the liver event CRF, and complete an SAE data collection tool if the event also meets the criteria for an SAE² Perform liver event follow up assessments Monitor the participant until liver chemistries resolve, stabilise, or return to within baseline (see MONITORING below) Viral hepatitis serology³ Obtain INR and recheck with liver chemistry assessment un transaminases values show do trend Obtain blood sample for pharmacokinetic (PK) analysi and lactate dehydrogenase (LI Fractionate bilirubin, if total be ≥ 2 x ULN 				
 MONITORING: If ALT ≥ 3 x ULN AND bilirubin ≥ 2 x ULN or INR > 1.5 Repeat liver chemistries (include ALT, AST, alkaline phosphatase, bilirubin) 	 Obtain complete blood count with differential to assess eosinophilia Record the appearance or worsening of clinical symptoms of liver injury, or hypersensitivity, on the AE report form 			

Liver Chemistry Stopping Criteria

assessments within 24 hours

- Monitor participants twice weekly until liver chemistries resolve, stabilise or return to within baseline
- A specialist or hepatology consultation is recommended

If ALT \geq 3 x ULN AND bilirubin \leq 2 x ULN and INR \leq 1.5:

- Repeat liver chemistries (include ALT, AST, alkaline phosphatase, bilirubin) and perform liver event follow up assessments within 24 to 72 hours
- Monitor participants weekly until liver chemistries resolve, stabilize or return to within baseline

- Record use of concomitant medications on the concomitant medications report form including acetaminophen, herbal remedies, other over the counter medications.
- Record alcohol use on the liver event alcohol intake case report form

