5.2 Baseline Definitions

For all endpoints (except as noted in baseline definitions) the baseline value will be the latest pre-dose assessment, including those from unscheduled visits. If time is not collected, Day 1 assessments are assumed to be taken prior to first dose and used as baseline. In part 1, baseline definitions are applicable to each period.

Parameter	Study Assessments Considered As Baseline				Baseline Used in
	Screening	Day -2	Day -1	Day 1 (Pre-Dose)	Data Display
Safety Data		•		•	
Vital Signs	Х	X*	X	X	Mean of replicate assessments on Day
ECG	Х	X*	Х	X	Mean of replicate assessments on Day
Laboratory tests	Х	X*	Х		Day -1

^{*} Vital Sign, ECG and laboratory tests are not collected at day -2 for Part 2.

Unless otherwise stated, if baseline data is missing no derivation will be performed and baseline will be set to missing.

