14.6 Appendix 6: Derived and Transformed Data

14.6.1 General

Multiple Measurements at One Time Point

- Mean of the measurements will be calculated and used in any derivation of summary statistics but if listed, all data will be presented.
- If there are two values within a time window (as per Section 14.3.1) the value closest to the target day for that window will be used. If values are the same distance from the target, then the mean will be taken.
- Participants having both High and Low values for Normal Ranges at any post-baseline visits for safety parameters will be counted in both the High and Low categories of "Any visit post-baseline" row of related summary tables. This will also be applicable to relevant Potential Clinical Importance summary tables.

Study Day

- Calculated as the number of days from First Dose Date:
 - Ref Date = Missing → Study Day = Missing
 - Ref Date < First Dose Date → Study Day = Ref Date First Dose Date
 - Ref Data ≥ First Dose Date → Study Day = Ref Date (First Dose Date) + 1

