14.7 Appendix 7: Reporting Standards for Missing Data

14.7.1 Premature Withdrawals

Element	Reporting Detail
General	Participant study completion (i.e. as specified in the protocol) was defined as participants who has received the study treatment per the protocol and who has completed all phases of the study including the follow-up visit. The study including the follow-up visit.
	The end of the study is defined as the last participant's last visit.
	Withdrawn participants will not be replaced in the study.
	All available data from participants who were withdrawn from the study will be listed and all available planned data will be included in summary tables and figures, unless otherwise specified.
	Withdrawal visits will be summarised as withdrawal visits.

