3.15.	Safety	AE1	Summary of Adverse Events Leading to Permanent Discontinuation of Study Treatment or Withdrawal from Study by System Organ Class and Preferred Term /by Overall Frequency – Part 1	IDSL	SAC [1]
3.16.	Safety	AE1	Summary of Adverse Events Leading to Permanent Discontinuation of Study Treatment or Withdrawal from Study by System Organ Class and Preferred Term /by Overall Frequency – Part 2	IDSL	SAC [1]
Laborat	ory: Chemistry	I			

Safety:	Safety: Tables							
No.	Population	IDSL / Example Shell	Title	Programming Notes	Deliverable [Priority]			
3.17.	Safety	LB17	Summary of Worst Case Chemistry Results to Potential Clinical Importance (PCI) Criteria Post-Baseline Relative to Baseline – Part 1	ICH E3	SAC [1]			
3.18.	Safety	LB17	Summary of Worst Case Chemistry Results to Potential Clinical Importance (PCI) Criteria Post-Baseline Relative to Baseline – Part 2	ICH E3	SAC [1]			
3.19.	Safety	LB1	Summary of Chemistry Changes from Baseline – Part 1	ICH E3 Includes Baseline values	SAC [1]			
3.20.	Safety	LB1	Summary of Chemistry Changes from Baseline – Part 2	ICH E3 Includes Baseline values	SAC [1]			
Labora	tory: Hematolo	gy						
3.21.	Safety	LB17	Summary of Worst Case Hematology Results to Potential Clinical Importance (PCI) Criteria Post-Baseline Relative to Baseline – Part 1	ICH E3	SAC [1]			
3.22.	Safety	LB17	Summary of Worst Case Hematology Results to Potential Clinical Importance (PCI) Criteria Post-Baseline Relative to Baseline – Part 2	ICH E3	SAC [1]			
3.23.	Safety	LB1	Summary of Hematology Changes from Baseline – Part 1	ICH E3 Includes Baseline values.	SAC [1]			
3.24.	Safety	LB1	Summary of Hematology Changes from Baseline – Part 2	ICH E3 Includes Baseline values.	SAC [1]			
Labora	tory: Urinalysis	3						
3.25.	Safety	LB15	Summary of Worst Case Urine Data Results Relative to Normal Range Criteria Post-Baseline Relative to Baseline – Part 1	ICH E3	SAC [1]			

Safety:	Tables				
No.	Population	IDSL / Example Shell	Title	Programming Notes	Deliverable [Priority]
3.26.	Safety	LB15	Summary of Worst Case Urine Data Results Relative to Normal Range Criteria Post-Baseline Relative to Baseline – Part 2	ICH E3	SAC [1]
3.27.	Safety	LB1	Summary of Urine Changes from Baseline – Part 1	ICH E3 Includes Baseline values.	SAC [1]
3.28.	Safety	LB1	Summary of Urine Changes from Baseline– Part 2	ICH E3 Includes Baseline values.	SAC [1]
Labora	tory: Abnormal	ities			

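### SAP 14.5.2 bars unscheduled visits from every summary table, so the worst-case, toxicity-grade and hepatobiliary laboratory tables can miss a maximum seen only on an off-schedule repeat

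*SAP*

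**What the plan says.** The Unscheduled Visits entry in SAP 14.5.2 has two parts. The first is "Unscheduled visits will not be included in summary tables and/or figures". The second is "All unscheduled visits will be included in listings". SAP 14.7.1 takes the same line for withdrawn participants, for whom "all available planned data will be included in summary tables and figures, unless otherwise specified".

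Among the safety tables in SAP 14.12.7 are displays whose purpose is to show an extreme over the whole post-baseline period. Tables 3.17 and 3.18 are titled "Summary of Worst Case Chemistry Results to Potential Clinical Importance (PCI) Criteria Post-Baseline Relative to Baseline". Tables 3.21 and 3.22 do the same for hematology, and Tables 3.25 and 3.26 do so for urine against normal ranges. Tables 3.29 and 3.30 summarise treatment-emergent laboratory grades. Tables 3.33 and 3.34 summarise emergent hepatobiliary laboratory abnormalities.

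The protocol produces readings outside the visit schedule. Under section 9.4.5, clinically significantly abnormal laboratory values "should be repeated until the values return to normal or baseline" or are no longer judged significant. Appendix 3 requires repeat liver chemistries after a liver event, within 24 hours or within 24 to 72 hours depending on the pattern, followed by twice-weekly or weekly monitoring.

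For baseline the SAP does admit such readings. Under section 5.2, "the baseline value will be the latest pre-dose assessment, including those from unscheduled visits".

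**The concern.** A table headed worst case that leaves out some post-baseline values shows the worst scheduled value. Repeat sampling is triggered by abnormal results, so the omitted readings come from the participants of most interest for safety. If the recheck is higher than the scheduled value that prompted it, the table understates the finding or shows none.

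Safety is a primary objective of Part 2 and a secondary objective of Part 1, and protocol 10.4.1 promises summaries of laboratory toxicity grade. The groups are small, so a single participant visibly changes a reported percentage. SAP 14.5.2 also keeps participant-level listings out of the main body of the study report, so a reader of the summary tables would not see the omitted value there.

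**Working it through.** There is no stated figure to reproduce; the check sets the rules against the schedule.

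**1. Does anything restore unscheduled values to these tables?**

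| Place | What it does |
|---|---|
| SAP 14.12.7, programming notes | None of the tables named above has a note admitting unscheduled values |
| SAP 14.5.2, General | The IDSL standards apply unless otherwise stated, and the unscheduled-visit rule states otherwise |
| SAP 14.6.1, time windows | Refers to windows in 14.3.1, which is marked not applicable, so no window moves an off-schedule sample to a scheduled visit |
| SAP 14.6.1, same time point | "Mean of the measurements will be calculated and used in any derivation of summary statistics"; this covers repeats attached to one time point, not a later recheck |
| SAP 14.6.1, any-visit post-baseline row | Counts high and low values at any post-baseline visit, but does not say that unscheduled visits are included |
| SAP Addendum, Table 2 | Marks Tables 3.1 to 3.46 as unchanged |

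Nothing in the documents restores them.

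**2. Can directed repeats fall between scheduled draws?** Chemistry days are from protocol Tables 2 and 3.

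- Part 1, after each dose: Days 2 and 4. After the last dose the next draw is follow-up, 7 to 14 days later, which is Days 8 to 15. The gap is 8 − 4 = 4 to 15 − 4 = 11 days. Between periods, a washout of at least 10 days puts the next dose on Day 11 or later, and its Day -2 sample on Day 9 or later. That gap is at least 9 − 4 = 5 days.
- Part 2, during dosing: Days 2, 4, 6, 8, 11 and 14. The intervals are 2, 2, 2, 3 and 3 days, or 48 to 72 hours.
- Part 2, after Day 14: follow-up 7 to 14 days after the Day 11 dose, which is Days 18 to 25. The gap is 18 − 14 = 4 to 25 − 14 = 11 days.
- Part 2 urinalysis is sparser: Days 2, 4, 11 and 14, with a gap of 11 − 4 = 7 days during dosing.

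A 24-to-72-hour liver repeat can coincide with the next scheduled draw during Part 2 dosing, or between Days 2 and 4 in Part 1, where that draw is 48 to 72 hours away. A within-24-hour repeat cannot coincide with a draw 48 hours or more away. After Day 4 in Part 1 and after Day 14 in Part 2, repeats at 24 to 72 hours, and weekly or twice-weekly monitoring, can fall wholly inside the gap.

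**3. Illustration with assumed values.** Suppose ALT is 1.8 × ULN on Day 4 of Part 1 and 3.2 × ULN on an unscheduled Day 6 recheck.

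- The SAP 14.8.1 limit for ALT is 2 × ULN or above. The scheduled value does not reach it and the recheck does. If the liver-function limits feed Table 3.17, that table shows no event for this participant.
- On the DAIDS scale in protocol Appendix 4, 1.8 × ULN is Grade 1 (1.25 to below 2.5) and 3.2 × ULN is Grade 2 (2.5 to below 5.0). If treatment-emergent, the participant is in Table 3.29, one grade too low.

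**4. Weight of one participant.** Part 1: 1/16 = 6.3% if all of the approximately 16 enrolled are in the Safety Population, and 1/12 = 8.3% at the minimum evaluable number. Part 2: 1/6 = 16.7% of the planned active group.

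**The case against.** The strongest reply is that little is lost. Unscheduled values remain in the listings, including all laboratory data for participants with a value of potential clinical importance (Listings 50 and 51) and Grade 2 or higher results (Listings 54 and 55). Under protocol 9.4.5 and Appendix 5, a clinically significant laboratory result is recorded as an adverse event, and the adverse event tables do not depend on visits. An ALT of 3.2 × ULN also triggers a liver event CRF. The analysis is descriptive, with no hypothesis tested. A repeat usually follows an abnormal scheduled value that is already in the tables, and many liver repeats during dosing can fall on a scheduled draw. The any-visit post-baseline wording in SAP 14.6.1 could be read as a more specific rule for these displays.

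All of this limits the consequence, and most of it stands. It does not remove the conflict. Listings and adverse event tables do not correct a worst-case count, and the any-visit wording does not expressly admit unscheduled visits.

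Some stronger readings are tempting but not supported:

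- That repeat ECGs are required. Protocol 9.4.3 leaves them to the investigator's judgement. The withdrawal criterion in 8.1.2 uses the average of triplicates while most post-dose ECGs are single, so extra readings are plausible, but that is as far as the text goes.
- That the QTc category tables (3.39 to 3.42) report a maximum over time. Their titles do not say so, and the standard shell is not in the documents.
- That peaks characteristically occur on repeats. They may, but nothing in the documents says that they do.
- That Tables 3.31 and 3.32 lose events. They summarise liver event reporting, for which there is a dedicated CRF, and nothing shows that a visit filter removes those records.
- That admitting unscheduled values at baseline but not afterwards biases towards fewer abnormalities. The handling is inconsistent, but an unscheduled baseline can be lower as easily as higher, and absolute limits do not depend on baseline.

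**Conclusion.** The point holds for ten laboratory tables: 3.17, 3.18, 3.21, 3.22, 3.25, 3.26, 3.29, 3.30, 3.33 and 3.34. As written, SAP 14.5.2 defeats their purpose whenever the highest post-baseline value or grade occurs only on an off-schedule repeat. The exposure is clearest in the 4-to-11-day gaps before follow-up in both parts and in the gap of at least 5 days between Part 1 periods.

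The size cannot be estimated from the documents, because the number of such repeats is unknown. The 6% to 8% (Part 1) and 17% (Part 2 active) figures give the weight of one participant and do not predict how often this happens. The conclusion rests on a literal reading of 14.5.2 and on the absence of any overriding note. The loss is confined to laboratory summary counts and does not extend to all reporting of the event.

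**What to change.** Amend SAP 14.5.2 to say that unscheduled values are excluded from by-visit summaries and from mean and box plots, but that all post-baseline values, scheduled and unscheduled, are used in:

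- Tables 3.17, 3.18, 3.21, 3.22, 3.25, 3.26, 3.29, 3.30, 3.33 and 3.34;
- any row counting any visit post-baseline;
- any maximum-post-baseline row of the QTc category tables (3.39 to 3.42), if those tables have one.

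The cost is one sentence and a changed record filter for the named displays, with no new data. The drawback is that participants who are rechecked more often contribute more readings to their maximum. A footnote to the tables can say so.

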14.5.3 Reporting Standards for Pharmacokinetic Data

Pharmacokinetic Concentration Data					
PC Windows Non- Linear (WNL) File	PC WNL file (CSV format) for the non compartmental analysis by Clinical Pharmacology Modelling and Simulation function will be created according to Standards for the Transfer and Reporting of PK Data using HARP. Note: Concentration values will be imputed as per GUI_51487				
Descriptive Summary Statistics, Graphical Displays and Listings	Refer to IDSL PK Display Standards. Refer to IDSL Statistical Principle 6.06.1. Note: Concentration values will be imputed as per GUI_51487 for descriptive summary statistics/analysis and summarized graphical displays only.				
Pharmacokinetic Para	ameter Derivation				
PK Parameter to be Derived by Programmer	The following PK parameters will be derived by the Programmer: C24, C τ , Ctrough. Ro[AUC(0- τ)], R(Cmax), R(C τ)				
Pharmacokinetic Para	Pharmacokinetic Parameter Data				
Is NQ impacted PK Parameters Rule Being Followed	No				
Descriptive Summary Statistics, Graphical Displays and Listings	Refer to IDSL PK Display Standards.				

Descriptive Summary Statistics				
Continuous Data	Refer to IDSL Statistical Principle 6.06.1			
Categorical Data	N, n, frequency, %			
Reporting of Pharmacokinetic Concentration Data				
Descriptive Summary	Refer to IDSL Statistical Principle 6.06.1			
Statistics	Assign zero to NQ values (Refer to GUI_51487 for further details)			

Reporting of Pharmaco	Reporting of Pharmacokinetic Parameters		
Descriptive Summary Statistics (Loge Transformed)	 N, n, geometric mean, 95% CI of geometric mean, standard deviation (SD) of logged data and between and or within geometric coefficient of variation (CVb/w (%)) will be reported. [1] Geometric mean = exp(mean log_e-transformed values) [2] CV_b (%) = √ (exp(SD²) - 1) * 100 (SD = SD of log transformed data) [3] CV_w (%) = √ (exp(MSE) - 1) * 100 (MSE = mean square error from mixed effect model of loge-transformed data). 		
All Parameters	N, n, mean, SD, median, minimum, maximum		
Summary Tables	The following PK parameters will not be summarised: %AUCex		
Listings	Additionally, include the first point, last point and number of points used in the determination of lambda_z for listings.		

Graphical Displays

- Refer to IDSL Statistical Principals 7.01 to 7.13.
- The same symbol and line type will be used across figures to represent a given treatment group. The placebo group will be displayed using symbol type=empty circle and line type= solid line and color=black.
- When line plots are presented with treatment groups overlaid, the x-values will be offset (jittered) so the data are not plotted on top of each other.
- X-axis variables of time and dose will be plotted as continuous numeric variables.

